8.7.1.2. Pharmacokinetic Parameters

Pharmacokinetic data collected in this study may be analyzed according to a separate PK Analysis Plan and reported separately from the primary study results.

8.8. Pharmacodynamics

Inhibition of dopamine receptors is associated with an increase in serum prolactin levels. This is because dopamine has an inhibitory effect on the anterior pituitary lactotrophs which secrete prolactin. Thus, prolactin levels will be measured in this study (as indicated in [Table 5](#)) to characterize the pharmacodynamic effects of NG101. Blood samples for serum prolactin assessment will be sent to the central laboratory [REDACTED]. Results of prolactin level measurements after the pre-dose assessment on Day 1 will remain blinded until database lock.

Note that during the following visits, study drug will be administered in the clinic:

- **Day 1:** first dose in the clinic, and second dose of the day in the clinic for those participants in the Intense PK subset
- **Week 1:** a dose in the clinic (ie, not necessarily the first dose of the day)
- **Week 2:** first dose of the day in the clinic
- **Week 12:** a dose in the clinic (ie, not necessarily the first dose of the day)

Table 5: Serum Prolactin Sampling Times

Study Day	All Participants (\pm Time window)	Intensive PK Subset (\pm Time window)
Screening Visit	Screening Visit	Screening Visit
Day 1	Predose ^a 1 hour (\pm 5 minutes) -- -- --	Predose ^a 1 hour (\pm 5 minutes) 2 hours (\pm 5 minutes) 3 hours (\pm 10 minutes) 6 hours (\pm 10 minutes)
Week 2 Visit	Predose ^a 1 hour (\pm 5 minutes) -- -- --	Predose ^a 1 hour (\pm 5 minutes) 2 hours (\pm 10 minutes) 3 hours (\pm 10 minutes) 6 hours (\pm 10 minutes)
Week 12 or E/D Visit	Predose ^a 1 hour (\pm 5 minutes)	Predose ^a 1 hour (\pm 5 minutes)
EoS / Follow-up Visit	EoS / Follow-up Visit	EoS / Follow-up Visit

Abbreviations: E/D = Early discontinuation; EoS = End of study; PK = pharmacokinetic

^a Within 15 to 20 minutes before dosing.

8.9. Genetics

Genetic research will be conducted in this study. A 5 mL blood sample will be collected for the analysis of one or more genes or genetic markers throughout the genome. Genetic analysis is noted as optional on the consent form, and participants will have the opportunity to consent or opt out without impacting their participation in the study.

In the event of DNA extraction failure, a replacement genetic blood sample may be requested from the participant.

See [Appendix 10.8](#) for information regarding genetic research. Details on processes for collection and shipment and destruction of these samples can be found in the Laboratory Manual.

8.10. Biomarkers

No additional biomarkers are planned to be evaluated in this study.

8.11. Immunogenicity Assessments

Immunogenicity will not be evaluated in this study.

8.12. Healthcare Resource Utilization

Health economics data associated with medical encounters will be collected in the CRF by the investigator and study-site personnel for all participants throughout the study. Protocol-mandated procedures, tests, and encounters are excluded.

The data collected may be used to conduct exploratory economic analyses and will include:

- Number and duration of medical care encounters, including surgeries, and other selected procedures (inpatient and outpatient)
- Duration of hospitalization (total days or length of stay, including duration by wards [eg, intensive care unit])
- Number and type of diagnostic and therapeutic tests and procedures
- Outpatient medical encounters and interventions (including physician urgent care clinic or emergency room visits, tests and procedures, and medications).

9. Statistical Considerations

9.1. Sample Size Determination

A total of approximately 280 participants will be randomized to achieve an estimated 224 participants completing the 12-week treatment period (and approximately 56 participants per treatment arm). At least 120 randomized participants will have diabetic gastroparesis and at least 120 randomized patients will have idiopathic gastroparesis. Up to approximately 140 participants can be cannabinoid users, and of these, approximately 56 can be marijuana users.

A sample size of 280 participants provides approximately 83% power to detect a mean treatment difference in the nausea severity score of 1.0 (on an 11-point scale) between an active dose group versus placebo at the 2-sided 0.05 significance level. This is based on a standard deviation of 1.8, a 20% drop-out rate, and a 2-sample t-test.

9.2. Populations for Analyses

The following populations are defined:

Population	Description
Enrolled	All participants who sign the ICF.
Intensive PK	All Enrolled participants who consented to the intensive PK sampling. Participants will be analyzed according to the study medication they actually received.
Intent-to-Treat (ITT)	All Enrolled participants who are randomized. Participants will be analyzed according to the study medication to which they were randomized.
Per Protocol (PP)	All participants in the ITT population who do not have any major protocol violations. Participants will be analyzed according to the study medication they actually received.
Safety	All participants who take at least 1 dose of study drug. Participants will be analyzed according to the study drug they actually received.

9.3. Statistical Analyses

The statistical analysis plan (SAP) will be finalized prior to unblinding and will include a more technical and detailed description of the statistical analyses described in this section. This section is a summary of the planned statistical analyses of the most important endpoints, including primary and key secondary endpoints.

9.3.1. General considerations

Continuous variables will be summarized using the number of observations, mean, standard deviation (SD) median, minimum, and maximum. Categorical variables will be summarized using frequency counts and percentages.

9.3.2. Efficacy Endpoints

The following algorithm will be applied to the daily GI assessments in the DIGS-DD and other GI assessments to create the baseline and weekly treatment period scores:

- A participant's baseline score will be the mean of the scores during the 2-week Pretreatment Period (ie, each weekly score is the mean of the daily scores)
- For each week in the 12-week Treatment Period, a participant's score for that week will be the mean of the daily scores for that week.
- Change from baseline for a particular week in the Treatment Period is that week's score minus the baseline score.
- If a participant has < 4 non-missing values for a week, the weekly score will be set to missing.

9.3.2.1. Primary Efficacy Endpoint

The primary efficacy endpoint is the change from baseline at Weeks 7 through 12 for the nausea severity score on the DIGS-DD (described in [Section 8.3.1](#)).

The primary efficacy endpoint will be analyzed using a mixed-effect model for repeated measures (MMRM) on the weekly mean change from baseline scores in the Treatment Period (ie, Weeks 1 through 12). The model will have treatment group, baseline nausea score, sex, gastroparesis etiology, cannabinoid use, study week, treatment group \times study week (interaction effect), baseline nausea score \times study week (interaction effect), sex \times study week (interaction effect), and gastroparesis etiology \times study week (interaction effect), and cannabinoid use \times study week (interaction effect) as fixed effects and participant as a random effect. The average value across Weeks 7 through 12 will be calculated for each treatment group using the MMRM along with the difference between each NG101 group versus the placebo group.

The primary analysis will be performed on the PP population using an observed-case analysis for handling missing data. For each NG101 group versus the placebo group, the average value across Weeks 7 through 12 will be tested at the 2-sided 0.05 level.

Subgroup analyses on the primary endpoint will be performed on the randomization stratification factors (sex, gastroparesis etiology, and cannabinoid use) to assess the consistency of treatment effect. Additional sensitivity and supportive analyses for the primary endpoint analysis will be provided in the SAP.

The primary analysis will not exclude or censor observations due to rescue medication use. Supplemental analyses which exclude observations due to rescue medication use will be detailed in the SAP.

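### The primary repeated-measures model names only a random participant effect; read literally, its Weeks 7–12 test holds the 5% level only under some weekly covariance patterns

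*Combined protocol and SAP*

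**What the plan says.** Section 9.3.2.1 fits a "mixed-effect model for repeated measures (MMRM) on the weekly mean change from baseline scores in the Treatment Period", that is, Weeks 1 to 12. The fixed effects are treatment, baseline nausea, sex, etiology, cannabinoid use and week, plus the interaction of each of the first five with week. The list ends "as fixed effects and participant as a random effect", and no other term describes dependence within a participant.

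Only the second half of treatment is tested: "The average value across Weeks 7 through 12 will be calculated for each treatment group using the MMRM". Each dose is compared with placebo at the two-sided 0.05 level. On population and missing data: "The primary analysis will be performed on the PP population using an observed-case analysis for handling missing data". Section 9.3.2 defines baseline: the participant's "baseline score will be the mean of the scores during the 2-week Pretreatment Period".

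Section 9.3 describes its own status: "This section is a summary of the planned statistical analyses of the most important endpoints, including primary and key secondary endpoints". It adds that the SAP "will include a more technical and detailed description of the statistical analyses described in this section". The combined document holds no separate SAP text on this model. Section 9.1 gives the only variability figure: "This is based on a standard deviation of 1.8, a 20% drop-out rate, and a 2-sample t-test". Section 9.3.3 carries the model over to the key secondary endpoints.

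**The concern.** A random participant effect with independent residuals implies one variance and one correlation for all pairs of weeks. With complete data and every fixed effect crossed with week, the estimated treatment difference does not depend on the covariance assumed, but its standard error does. Compound symmetry estimates that standard error from variance and covariance averaged over 12 weeks, while the contrast uses only the last six.

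The baseline term makes this matter more. Baseline comes from the two weeks just before treatment. If correlation decays with time and raw variance is stable, baseline explains early weeks better than late ones, so residual variance rises towards Weeks 7–12 and pooling understates it. If raw variance falls during treatment, the effect is offset or reversed.

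At stake are the standard error and p-value of each of the three primary comparisons, in a study meant to guide the phase 3 dose. Two analysts following the same text, one fitting a random intercept and one an unstructured covariance, could report different p-values.

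**Working it through.** **The plan's own figure.** Inputs from Section 9.1: difference 1.0, SD 1.8, 280 randomized in four arms (70 each), 20% dropout, so 70 × 0.8 = 56 per arm. Noncentrality = 1.0 / (1.8 × √(2/56)) = 2.94. With 110 degrees of freedom and two-sided 0.05, power is 83.0%, as stated. It rests on a two-sample t-test and does not involve the weekly covariance.

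**Formulas (complete data).** Let v and c be the mean variance and mean covariance over the 12 weeks.

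- Variance the model assigns to the Weeks 7–12 mean: c + (v − c)/6.
- True variance: sum of the 6 × 6 block for Weeks 7–12, divided by 36.
- SE ratio = √(model/true).
- Actual level = 2 × (1 − Φ(1.96 × SE ratio)).

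**Example without baseline adjustment.** AR(1), correlation 0.9, unit variance: v = 1 and c = 0.658. Model: 0.658 + 0.342/6 = 0.715. True: 0.824. SE ratio: √(0.715/0.824) = 0.93. Level: 6.8%.

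**Example with baseline adjustment.** Assume raw weekly variance 1, made up of 50% stable, 30% AR(1) with rho 0.8, and 20% week-specific noise. The correlation at lag k is 0.5 + 0.3 × 0.8^k. The variance of the two-week baseline mean is (1 + 0.74)/2 = 0.87.

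- Week 1: covariance with baseline (0.740 + 0.692)/2 = 0.716. Residual variance 1 − 0.716²/0.87 = 0.41.
- Week 12: covariance with baseline (0.521 + 0.516)/2 = 0.519. Residual variance 1 − 0.519²/0.87 = 0.69.

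Over the whole conditional matrix, v = 0.604 and c = 0.242. Model: 0.242 + 0.362/6 = 0.302. True: 0.409. SE ratio: 0.86. Level: 9.2%.

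**Range of patterns.** The documents give no weekly SDs or correlations, so these are assumptions. The grid has 101 lag-decay patterns. Ninety-five have stable share 30–70%, noise 0–30%, AR share the remainder (at least 10%) and rho 0.5–0.9. Six are pure AR(1), rho 0.5–0.95. In the last two rows, the raw SD falls linearly from Week 1 to Week 12.

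| Assumed truth | Actual level |
|---|---|
| Compound symmetry | 5.0% |
| Lag decay, constant residual variance | 5.1–9.2% |
| Lag decay, constant raw variance, baseline-adjusted | 5.9–12.9% (SE ratio 0.96 to 0.775) |
| Same, raw SD falling 10 / 20 / 30% | 5.2–12.1 / 4.5–11.3 / 3.7–10.3% |
| Constant or weakly decaying correlation, raw SD falling 20–40% | 2.3–5.5% |

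**Simulation under no treatment effect.** REML random-intercept fit with all 96 fixed-effect parameters. Assumed: 25% male, 50% diabetic, 50% cannabinoid users, no covariate effects. Three contrasts per run; 10,000 runs with 224 complete participants, and 2,000 runs with 280 randomized and 20% completely random dropout. Each cell gives constant raw SD / 20% fall.

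| Stable/AR/noise | Complete data | With dropout |
|---|---|---|
| 60/10/30, rho 0.5 | 6.1 / 4.5% | 6.1 / 4.3% |
| 50/30/20, rho 0.8 | 9.3 / 7.4% | 10.5 / 8.3% |
| 70/30/0, rho 0.9 | 12.8 / 11.2% | 15.3 / 14.0% |
| Constant correlation 0.7 | 5.3 / 3.7% | 5.3 / 3.9% |

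With complete data, the equivalent of an unstructured fit is an ANCOVA on each participant's Weeks 7–12 mean. It gave 4.9–5.3% in all eight complete-data settings. It was not run with dropout.

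**The case against.** Section 9.3 calls itself a summary and assigns technical detail to a SAP finalized before unblinding; residual covariance and degrees of freedom are such detail. The label MMRM is often used for an unstructured covariance, and the participant term may only mark the repeated-measures unit. If so, none of the error rates above applies. This stands, and it is why the finding is conditional. It does not remove the point, because the section assigns sensitivity and rescue-medication analyses to the SAP by name but gives the primary model term by term, and the term it gives specifies compound symmetry.

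The size is also open to challenge. Of the 101 baseline-adjusted patterns, 68 reach 8% when raw variance is constant, but only 50, 31, 15 and 7 do when the raw SD falls by 10, 20, 30 and 40%. At a 40% fall the median is 5.1%. Week-specific noise matters too: with constant raw variance, 30 of 31 patterns without it reach 8%, against 6 of 20 with 30% noise. These counts describe the grid and are not probabilities. That is correct, and no single inflation figure should be quoted for this trial.

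Finally, the unstructured fit and Kenward-Roger were not simulated with dropout, and convergence is a genuine risk. Another named structure with an empirical standard error would also be defensible.

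**Conclusion.** The concern holds as a conditional finding. As written, the only dependence term implies compound symmetry, and the primary test is then sure of its level only if that structure is true. Under the patterns examined with complete data, the actual level runs from 2.3% to 12.9% against a nominal 5%. With baseline adjustment, lag decay and constant raw variance, the standard error is about 4% to 22.5% too small. With falling variance and near-constant correlation, the test is close to nominal or conservative. The documents cannot say which case applies. Random dropout of 20% raised the error in the two stronger-decay simulations and changed it little in the other two. Sample size and the 83% power are unaffected.

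**What to change.** Replace the random participant term with an unstructured within-participant covariance across Weeks 1–12 and Kenward-Roger degrees of freedom. State an ordered fallback for non-convergence before unblinding, for example heterogeneous Toeplitz, then a simpler structure with an empirical standard error. If the present wording only identifies the repeated-measures unit, naming the covariance settles the matter. Apply the same text to the key secondary endpoints that use this model; the vomiting-episode count was not examined here.

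The cost is one or two sentences in the protocol or SAP, plus a heavier model: 12 × 13/2 = 78 covariance parameters and 8 × 12 = 96 fixed-effect parameters. These are estimated in a per-protocol population smaller than 280, with about 224 completers expected. Non-convergence is a real possibility, so the fallback order must be fixed in advance.

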6.5.1. Rescue Medicine

The study site will supply anti-emetic rescue medication that will be provided by the sponsor. The following rescue medications may be used:

- Ondansetron (4 mg tablet)
- Promethazine (25 mg tablet)

The use of rescue medications is allowed up to 2 times daily during the Pretreatment Period and the Treatment Period, except on the day prior to (within 24 hours) and the day of clinic visits.

Participants will be instructed to use rescue medication only during a day when nausea or vomiting is intolerable. For participants taking ondansetron, a second 4 mg tablet may be taken 1 hour after the first dose if there has been insufficient relief of nausea; thus, participants are allowed up to 4 tablets (16 mg) per day.

Participants are required to use only the study-provided rescue medications. Use of rescue medication will be captured in the daily diary; compliance with regard to rescue medication will be assessed at each study visit and captured in the source documents. As described in [Section 9.3.4](#), weekly use of rescue medication will also be assessed as an additional secondary endpoint.

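### The primary test, and by extension the key secondaries, run on a per-protocol set grouped by drug received, and the supplied text gives the as-randomised ITT set no efficacy analysis

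*Combined protocol and SAP*

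**What the plan says.** Section 9.3.2.1 assigns the primary mixed-model analysis to the per-protocol (PP) set: "The primary analysis will be performed on the PP population using an observed-case analysis for handling missing data". Each NG101 dose is tested against placebo at the two-sided 0.05 level.

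Section 9.2 defines PP as "All participants in the ITT population who do not have any major protocol violations" and adds "Participants will be analyzed according to the study medication they actually received". For the ITT set, which is everyone randomised, the rule is "Participants will be analyzed according to the study medication to which they were randomized". After that definition ITT appears again only in the abbreviation list.

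Section 9.3.3 handles the key secondary endpoints in the same way as the primary. The only difference it names is the baseline covariate, so PP carries over by implication.

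Two sentences defer detail. Section 9.3 says "The statistical analysis plan (SAP) will be finalized prior to unblinding and will include a more technical and detailed description of the statistical analyses", and section 9.3.2.1 says "Additional sensitivity and supportive analyses for the primary endpoint analysis will be provided in the SAP". Neither names an analysis set. The supplied text contains no separate SAP body.

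On rescue, section 9.3.2.1 states "The primary analysis will not exclude or censor observations due to rescue medication use".

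**The concern.** Randomisation makes the arms comparable as assigned. A set defined by the absence of violations is partly chosen by what happens afterwards. If the reasons for exclusion are related to outcome and occur at different rates across arms, the comparison no longer has that protection.

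Several rules that could generate violations govern behaviour during treatment. Section 6.5.1 limits how often rescue may be taken, allows only study-supplied products, and ties use to bad days: "Participants will be instructed to use rescue medication only during a day when nausea or vomiting is intolerable". Exclusion criterion 11 (section 5.2) bars an increase in cannabinoid use. A participant whose nausea is uncontrolled is plausibly more likely to breach such rules. If those breaches count as major, PP removes the whole participant, although section 9.3.2.1 says that rescue use will not remove observations. The documents do not say whether they count.

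Not every exclusion is a problem. Removing participants for eligibility breaches that predate randomisation carries less risk. Grouping by drug received matters only where dispensing went wrong, which central IRT assignment (section 6.3) makes unlikely. The PP restriction is the main issue.

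**Working it through.** **Inputs from section 9.1.** SD 1.8, difference 1.0, two-sided 0.05, two-sample t-test, 280 randomised 1:1:1:1 (70 per arm), 20% dropout (56 per arm).

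**The plan's own figure.** SE = 1.8 × √(2/56) = 0.340, so the noncentrality is 1.0/0.340 = 2.94. Noncentral-t power is 83.0%, which agrees with the stated 83%.

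**Assumed inputs.** The documents give no violation rate. Let one arm of a pair lose a fraction f more than the other, with f = 5%, 10% or 15% (about 3, 6 or 8 of 56). Let those removed average d = 1, 1.5 or 2 points worse than their full arm mean. Then:

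- Shift in the retained arm mean = f × d / (1 − f)
- SE = 1.8 × √(1/56 + 1/(56(1 − f))) = 0.3446, 0.3495, 0.3549 for f = 5%, 10%, 15%
- Two-sided type I error with no true effect = P(|Z + shift/SE| > 1.96)

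**Active arm affected, no true effect.** Each cell gives the shift, then the type I error.

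| f | d = 1 | d = 1.5 | d = 2 |
|---|---|---|---|
| 5% | 0.053; 5.3% | 0.079; 5.6% | 0.105; 6.1% |
| 10% | 0.111; 6.2% | 0.167; 7.6% | 0.222; 9.7% |
| 15% | 0.176; 7.9% | 0.265; 11.6% | 0.353; 16.9% |

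Worked cell (f = 10%, d = 2): shift = 0.10 × 2/0.90 = 0.222, and 0.222/0.3495 = 0.636. P(Z > 1.96 − 0.636) + P(Z < −1.96 − 0.636) = 9.7%. With the noncentral t in place of the normal, the range across the table is 5.3% to 16.7%.

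**Placebo arm affected, true difference 1.0.** The expected estimate is 1 − shift. Power is by noncentral t.

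| f, d | Expected estimate | Power | Power at the same sizes, no bias |
|---|---|---|---|
| 5%, 1 | 0.947 | 77.8% | 82.0% |
| 10%, 1.5 | 0.833 | 65.6% | 80.9% |
| 15%, 2 | 0.647 | 43.9% | 79.7% |

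**Starting point.** Taking 70 per arm instead of 56, for the case where dropouts contribute early data, type I error is 5.3% to 19.9% and the reverse-direction power is 86% to 52.5%. The pattern is the same.

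**Power under ITT.** It is 83.0% if 20% contribute no data (56 per arm) and 90.4% if all 70 per arm contribute at a difference of 1.0. It falls to about 74% if all 70 contribute but the difference is diluted to 0.8. The 0.8 is an assumption.

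**The case against.** The strongest reply is that section 9.3 calls itself a summary and leaves detail to an SAP finalised before unblinding. That SAP may define major violations and include an ITT analysis. This stands as a limit on what can be said about absence, which is why the point is confined to the supplied text. It does not answer the main point, because a supportive ITT analysis would leave PP as the deciding test.

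The rescue route is conjecture: no text classes a rescue breach as major, and the sentence on rescue observations points the other way. That is fair, and it is a reason for the plan to say so explicitly.

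The sizes are assumed. In the upper corner those removed are 2 points worse than their arm mean, more than one SD, with 15% more lost in one arm than in the other. Dropouts and violators may also overlap. This stands: the figures are scenarios, and the direction is unknown.

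This is a phase 2 study with no stated adjustment across three doses, which looks more like learning than confirming. But its results are meant to choose the phase 3 dose, so the meaning of the primary comparison still matters.

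Finally, sections 1.1 and 4.1 send anyone who stops drug permanently to an early discontinuation visit and then a follow-up visit two weeks later. If diaries stop then, ITT mainly restores violators and recovers few later scores. This also stands: 90.4% power is a best case.

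**Conclusion.** The concern holds and should be fixed before unblinding. The primary set is PP, its membership turns on an undefined term, and ITT has no assigned efficacy role in the supplied text. Extending this to the key secondaries is an inference from section 9.3.3, though the natural one.

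If exclusions are balanced or unrelated to outcome, little bias results. If they are differential and outcome-related on the assumed scale, the distortion runs from trivial to serious in either direction. No sample-size figure in the plan is wrong.

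Two secondary points need clarification:

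- No supplied text says whether eDiary scores are collected after study drug stops. The DIGS-DD row of the schedule of activities lost its cell marks in extraction, so check the source table first.
- Section 7.1 opens by keeping participants who stop drug in the study, while its orthostatic-hypotension item withdraws them from the study. These statements must be reconciled.

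**What to change.** 1. In section 9.3.2.1, replace the analysis-set sentence with wording such as: *The primary efficacy analysis uses the ITT population, with each participant counted in the arm assigned at randomization.* Apply the same set to the key secondaries in section 9.3.3, and make PP supportive.
2. Define major protocol violation in section 9.2 or the SAP. State how breaches of the rescue rules are treated, in line with the statement on rescue use in section 9.3.2.1.
3. Fix PP membership blind, before any unblinding, including the optional group-level interim in section 9.4.
4. State whether eDiary scores are collected after study drug stops. If they are, include them in the ITT mixed model.
5. Reconcile the two statements in section 7.1.

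The cost is protocol and SAP wording, plus continued diary use if collection after discontinuation is chosen. The statistical price is possible dilution of the estimate, with the power consequences shown in the working.
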